8.4 Exclusion Criteria

Subjects will be excluded if they meet any of the following criteria:

- a. If subject's age is less than 18 or older than 55 years.
- b. Have any history of allergy or hypersensitivity to Paroxetine or to any of its metabolites/derivatives or related drugs or excipients.
- c. Have a positive test result for hepatitis B surface antigen (HBs Ag) or hepatitis C virus antibody (HCV Ab) or HIV antibodies (types 1 and 2) or VDRL.

Bioequivalence Pivotal Study Protocol of Paroxetine tablets 20 mg under fasting conditions.

- d. Subjects with symptoms suggestive of active COVID-19 infection (i.e. fever, cough, respiratory difficulties) within 14 days of inpatient admission.
- e. Subjects with known COVID-19 positive contacts* within the past 14 days prior to the first period check-in.

*Positive Contact; this means, if the subject has been living, providing, care, being within 1.5 m for at least 15 min or having exposure to respiratory secretions with/to a person who has COVID-19.

- f. Study drug is contraindicated for medical reasons to the subject as per protocol section 3.7.
- g. Have any history or presence of significant cardiovascular, pulmonary, hepatic, renal, gastrointestinal, seizures, endocrine, dermatological, neurological or psychiatric disease or disorder (e.g. Subjects with uncontrolled hypertension, phaeochromocytoma, carcinoid, thyrotoxicosis, bipolar depression, schizoaffective disorder and acute confusional states).
- h. Presence of significant gastrointestinal, hepatic or kidney disease, or surgery or any other conditions known to interfere with the absorption, distribution, metabolism or excretion of drugs or known to potentiate or predispose to undesired effects.

Or

Subjects with a history of gastrointestinal disorder or surgery which may affect the absorption of investigational drug.

- i. Have a history of alcohol abuse or drug abuse during the last 1 year prior to period-1 dosing.
- j. Have a history of smoking \geq 10 cigarettes per day during the last 6 months prior to period-1 dosing.
- k. Have history or presence of cancer.
- l. Have any history of gastrointestinal ulcers / intestinal bleeding.
- m. Have difficulty in swallowing solid medications such as tablet.
- n. Have history of difficulty for donating blood.

Bioequivalence Pivotal Study Protocol of Paroxetine tablets 20 mg under fasting conditions.

- o. Have clinically significant abnormal laboratory tests results.
- p. Have a systolic blood pressure < 90 or > 140 mmHg or diastolic blood pressure is < 60 or > 90 mmHg.
- q. Have a pulse rate < 60 beats/minute or > 100 beats/minute (Lower range of pulse range will be accepted up to 45 beats/minute in case of athlete).
- r. Have used any prescribed medication during the last 14 days preceding the first dosing, or use OTC, medicinal or herbal products during the last 7 days or use medicinal enzyme inhibitors / inducers during last 30 days preceding the first dosing.
- s. Have participated in a drug research study or donated blood within the last 3 months.
- t. Have a positive result for drugs of abuse test [Cannabinoids (Marijuana/Tetrahydrocannabinol-THC), Cocaine, Opiates/Morphine, Amphetamine, Methamphetamine and Benzodiazepines] performed during screening.
- u. Female subject, who is currently breast feeding or a who is pregnant or who is likely to become pregnant during the study.
- v. Female subject has a positive pregnancy test results.
- w. Unwillingness or inability to comply with the instructions on the lifestyle described in this Protocol.
- x. If the PI considers, for any reason, that the volunteer is not a suitable candidate to receive the study drug.

8.5 Criteria for Subject Withdrawal from the Study

Subjects have the right to withdraw their consent from the study at any time and for any reason without facing any related prejudice. The Principal Investigator may withdraw a subject from the study if:

Bioequivalence Pivotal Study Protocol of Paroxetine tablets 20 mg under fasting conditions.

- a. The subject wishes to withdraw consent (In case the subject request to disposal of the collected samples, the same shall be documented and will be informed to sponsor and REC/RC).
- b. The subject suffers from significant inter-current illness or undergoes surgery during the study. In case a subject is positive for COVID-19 or has a related symptom (i.e. fever, cough, respiratory difficulties), they shall be isolated for 14 days and they shall be discontinued. In case any other subject was exposed to a COVID-19 patient, they must report this to Avant Santé, GSK and/or their primary care provider.
- c. Subject fails to comply with the requirements of the protocol section 9.3 Restrictions.
- d. Subject experiences an adverse event and it is not in the subject's best interest to continue in the study (as judged by the PI).
- e. Subject has a positive result for the breath alcohol test or urine drugs of abuse test [Cannabinoids (Marijuana/Tetrahydrocannabinol-THC), Cocaine, Opiates/Morphine, Amphetamine, Methamphetamine and Benzodiazepines] prior to check-in of each study period.
- f. The subject vomits at the time of the drug administration or vomiting / diarrhea occurs within 10 hours of drug administration (representing twice the median T_{max} of 5 hours).
- g. In case of a female subject a positive result for the pregnancy test.
- h. Subjects who miss 4 or more consecutive blood draws in any of the study periods.
According to NOM-177-SSA1-2013, section 8.9.5, frequent sampling points are needed around the T_{max} and also at least four samples during the log-terminal phase to obtain the extraction rate constant. If any subject misses 4 or more consecutive sampling points during the absorption phase or the extraction phase, it will have an impact on the precise accuracy of the C_{max} and AUC curve.
- i. The study is suspended or terminated by the sponsor or PI or EC/REC.

Bioequivalence Pivotal Study Protocol of Paroxetine tablets 20 mg under fasting conditions.

It should be noted that any subject that is not discontinued or withdrawn from the study will be considered as a subject who finishes the study.

9.0 TREATMENT OF SUBJECTS

9.1 Drug Administration

In each study period, all subjects will be required to fast overnight for at least 10.00 hours prior to dosing until at least 04.00 hours post-dose.

In each study period, a single-dose of either the test product (A) or reference product (B) will be orally administered to the subjects in sitting posture along with 250 mL of water at room temperature under fasting conditions.

The administration of the test or reference products to each subject will be performed as per a randomization schedule.

The subjects will be instructed to swallow the tablet as a whole as mentioned in the prescribing information and not to touch the tablet with their hands, chew or crush the tablet since this can affect the drug release.

Subject's hands and mouth will be checked after dosing to ensure compliance with dosing.

Immediately after dosing in each period trained study personnel will evaluate the compliance by supervising the complete administration procedure (SOP CP020, Administration of the Investigational Product).

Drug administration will be registered in the respective source documents.

9.2 Dietary Plan

Subjects will be provided with standard meals throughout their stay in the facilities.

On the check-in day (day -1) they will receive dinner, which will be finished at the latest 10.00 hours prior to dosing at the following day in each study period.

Subjects will be required to fast overnight for at least 10.00 hours prior to dosing and until at least 04.00 hours post-dose in each study period.

Bioequivalence Pivotal Study Protocol of Paroxetine tablets 20 mg under fasting conditions.

After the dose administration of test or reference product (day 1), lunch, snack and dinner will be provided at 04.00, 08.00 and 12.00 (with a grace period of + 45 minutes) hours post-dose respectively, in each study period.

The meal plan will be uniform for all the subjects and same between the study periods.

Information on the amount of meal consumed and the time of consumption by each subject will be registered in the respective source documents. The nutritional value of the meals is presented in the following table.

Table 5 Nutritional value of diet on study day 1

Nutritional Value of meals	
2000 kcal ± 10%	Calories (%)
Proteins	15-20%
Lipids	25-30%
Carbohydrates	50-60%
Total	*100%

*% of kilocalories is within its adequate distribution of 90–110%.

9.3 Restrictions

- **Smoking**

All subjects will be instructed to refrain from smoking of cigarettes / nicotine containing products for at least 72.00 hours prior to the dosing and until the last sample collection in each period and will be prohibited from smoking during their in-house stay.

- **Medications**

All subjects will be asked about their medication history. They will be instructed not to take any medication until the study is completed; particularly during the last 14 days preceding the first dosing for any prescribed medication, the last 7 days before for OTC medicinal or herbal products used for therapeutic purposes, and the last 30 days before for any enzyme inhibiting / inducing drugs preceding the first dosing.

Bioequivalence Pivotal Study Protocol of Paroxetine tablets 20 mg under fasting conditions.

Subjects will be specifically reminded that the restriction mentioned above includes analgesics, cold & anti-allergic preparations, vitamins and natural products used for therapeutic benefits and antacid preparations.

Vitamins used as nutritional supplements in non-therapeutic doses (as judged by the principal investigator or designee) may be accepted, but their consumption must be stopped from at least 7 days prior to the dosing and until the study is completed.

If a drug therapy other than that specified in the protocol is required prior to, during the study or in the washout period, the Principal Investigator shall decide whether to continue or discontinue the subject's participation based on the following:

- The pharmacology and pharmacokinetics of the non-study medication.
- The likelihood of a drug–drug interaction, which may affect the pharmacokinetic comparison of the study drugs.
- The time and duration of administration of the non-study medication.

• Diet

All subjects will be instructed to avoid the consumption of any xanthine-containing food or beverages (tea, coffee, theobromine, theophylline, chocolates, cola drinks, etc.) at least 72.00 hours prior to the dosing and until the last blood sample collection in each study period.

Subjects will be instructed to avoid the consumption of alcohol (or related products) as well as smoked or carbon cooked food from at least 72.00 hours prior to the dosing, until the last blood sample collection in each study period.

Subjects will be instructed to avoid the consumption of pomelos or grapefruit juice or products containing grapefruit extract (e.g. soda) from at least 72.00 hours prior to the dosing, and till the last blood sample collection in each study period.

The consumption of above-mentioned products will also be prohibited during their in-house stay.

Bioequivalence Pivotal Study Protocol of Paroxetine tablets 20 mg under fasting conditions.**Fluid (water) restriction**

The subjects will not be allowed to drink water 1 hour before and until 2 hours post-dose except for the 250 mL of water provided for the dosing, unless it is clinically indicated; at all other times water will be provided *ad libitum*.

Postural (activity) Restriction

The dose will be administered to all subjects at the scheduled time and subjects will be instructed to remain in comfortable sitting position for the first 02.00 hours following the drug administration except when clinically indicated or protocol specified activity (blood sample collection) or due to natural exigencies.

After 02.00 hours post-dose, subjects will be allowed to wander and will be advised to avoid any severe physical exertion.

In case of an adverse event (AE), subjects will be maintained in the proper position as per physician's assessment in each study period.

• Recommendations during washout period and visits to the center (ambulatory samples)

In case a subject has symptoms of COVID-19, the following recommendations will be provided (the same as dictated by the WHO):

- Isolation for 14 days at home: Staying at home except to get medical care immediately if having an emergency warning sign (i.e., trouble breathing).
- Monitoring temperature: average human body temperature is 36-37°C.
- Any related-COVID-19 symptom, worsening or recovery, must be reported to their primary care provider and to Avant Santé Principal Investigator.

9.4 Housing

Subjects will be in the clinical facility from at least 10.50 hours prior to the dosing until the last in-house blood sample collection i.e. 24 hours in each study period.

Subjects will visit clinical facility at 36.00, 48.00 and 72.00 hours for the collection of the ambulatory samples in each study period.

Bioequivalence Pivotal Study Protocol of Paroxetine tablets 20 mg under fasting conditions.

Subjects will be instructed to self-quarantine during the outpatient period of the study i.e. until 72 h blood sample collection in period-2 or until withdrawal, whichever is earlier, and to monitor at home their daily body temperature.

9.5 Sampling Schedule

In each study period, a total of 24 blood samples (4 mL each) will be collected from each subject as per the following schedule:

- The first blood sample will be collected within 1.50 hours prior to the dosing (00.00 hours / pre-dose).
- The remaining samples will be collected after the dosing of the test or reference drug at 00.50, 01.00, 01.50, 02.00, 02.50, 03.00, 03.50, 04.00, 04.50, 05.00, 05.50, 06.00, 06.50, 07.00, 08.00, 09.00, 10.00, 12.00, 16.00, 24.00, 36.00, 48.00 and 72.00 hours.
- The samples corresponding to 36.00, 48.00 and 72.00 hours post dose will be collected on separate visits as ambulatory sample in each period of the study.

The total blood volume collected from each subject will not exceed 223 mL, which includes about 10 mL for the selection process (selection and enrollment), 21 mL for the discarded heparinized blood and 192 mL for the pharmacokinetic evaluation.

If circumstances arise, where more than 223 + 10 mL (may be collected for safety evaluation purpose) of blood from each subject needs to be withdrawn the subject will be asked for additional consent and the REC / RC will be informed.

Table 6 Blood volume of samples to be collected during the study

Sample Type	Sample Volume (mL)	Number of Sampling Times			Total Volume (mL)
		Screening	Study Period	Follow-Up	
Screening	10 mL	1	-----	-----	10
PK Blood Samples	4 mL	-----	48 samples (Period 1,2)	-----	192
Heparinized blood	0.5 mL	-----	42 samples (Period 1,2)	-----	21

Bioequivalence Pivotal Study Protocol of Paroxetine tablets 20 mg under fasting conditions.**TOTAL****223**

At the time of each blood sample collection, 4 mL will be collected through an indwelling cannula placed temporarily (for at least 24.00 hours post-dose) in a forearm vein or as per subject's convenience for practical reasons and the remaining sample(s) will be collected through direct venipuncture.

Blood samples will be obtained in K₂-EDTA vacuum tubes (pre-labeled with project number, period number, subject number and sample number).

If the times of sample collection vital signs or medical examination and food consumption overlap during the housing period, the order will be as follows.

Sample collection → vital signs or medical examination → food consumption.

Blood samples shall be collected not earlier or later than (\pm) 2 minutes of the specified sampling time for all the in-house samples and not earlier or later than (\pm) 60 minutes of the specified sampling time for ambulatory samples. Blood sampling will be registered in the respective source documents.

If blood samples are collected earlier or later than this period from the scheduled time, this shall be reported as a deviation from this protocol.

Heparin-lock technique (with 0.5 mL) will be used to prevent coagulation of the blood in the cannula. Prior to the blood collection through the cannula, 0.5 mL of heparinized blood will be withdrawn and discarded in order to prevent the heparin interfering with the sample analysis. If for any reason the indwelling cannula is blocked or removed, direct venipuncture will be performed to collect the samples.

All this process is described in detail in the procedure CP021 (Phlebotomy Performance).

If any subject misses any blood sampling point, it will be considered as missing sample.

The same will be denoted as (M), it will be considered as protocol deviation and mentioned in the clinical study report.

Bioequivalence Pivotal Study Protocol of Paroxetine tablets 20 mg under fasting conditions.

9.6 Sample Processing and Storage

Once collected, the blood samples will be placed in an ice-filled container or another cooling device until the centrifugation process is started.

Centrifugation process will be started within 45 minutes from the time of blood sample collection and will be performed at 3000 rpm for 10 minutes at 4 ± 2 °C.

The plasma obtained from blood samples will be transferred as soon as possible into two different cryo-tubes (aliquot 1 and aliquot 2), pre-labeled with project number, period number, subject number, sample number and aliquot number.

The plasma volume obtained from blood sample will be allocated as follows:

Aliquot 1: 1.0 mL of plasma (approximately).

Aliquot 2: rest of the plasma.

All plasma samples (aliquot 1 for sample analysis and aliquot 2 as back-up) will be stored in the Clinical facility at a temperature of -50 °C or below until transferred in dry ice to the Bioanalytical facility, where they will be stored at a temperature of -50 C or below until their analysis.

9.7 Sample transfer

At the end of each period or clinical phase, samples will be separated and sorted by subject, period and aliquot as per the procedure CP031 (Biological Samples Processing, Storage, Shipment and Spillage Handling). Once the samples of each subject are sorted, they will be placed in propylene storage containers or in an auto-sealed bag, previously labeled with the project number, period number, subject number, aliquot number and number of samples.

Process of separation, sorting and sample verification will be done with sufficient dry ice. Temperature will be monitored during the separation sorting and verification process with a calibrated data-logger and under supervision of quality assurance department personnel.

At the end of the clinical phase of the study or each study period, aliquot 1 (used for the quantification and re-analysis) samples will be shipped for analysis to the Bioanalytical

Bioequivalence Pivotal Study Protocol of Paroxetine tablets 20 mg under fasting conditions.

facility in a container with dry ice while transfer and temperature will be monitored. The aliquot 2 (for back-up) samples will be shipped using the same procedure and only after confirming the reception or loss of the aliquot 1 samples. If required, Aliquot 2 will be used. Aliquots will be stored in different deep freezers under the same condition in bioanalytical area.

The process of reception, handling, storage and disposal of biological samples in the Bioanalytical unit, will be carried out according to procedure BL021 (Reception, Management, Storage, Transfer and Disposition of Biological Samples).

CP personnel shall send the information "subjects samples to be analyzed" (including the reason or justification for not analyzing other samples of subjects) to the Bioanalytical department with the approval of the Principal Investigator and authorized by QA.

10.0 ASSESSMENT OF EFFICACY

As this is a bioequivalence study, no efficacy assessment will be performed. The pharmacokinetic parameters of the test and reference formulations will be assessed.

11.0 ASSESSMENT OF SAFETY (CLINICAL SAFETY MEASURES)**11.1 Recording of Vital Signs and Medical Examination**

Medical examination, which consists on subject's anamnesis, inquiry for possible AEs, evaluation of vital signs and overall health status to determine if further physical examination is required will be performed before check-in, prior to the dosing and before the check-out in each study period.

Nevertheless, it may also be performed at any time during the study conduction if judged necessary by the physician.

Physical examination, which consists on subject's anamnesis, examination of the head, neck, thorax, abdomen, and extremities (but not limited), inquiry for possible AEs and evaluation

Bioequivalence Pivotal Study Protocol of Paroxetine tablets 20 mg under fasting conditions.

of vital signs will be performed before check-in of each study period and may also be performed at any time during the study conduction if judged necessary by the physician.

Vital signs (sitting blood pressure, pulse rate, respiratory rate and axillary body temperature) will be measured and registered before check-in, prior to dosing, at 03.00, 05.00 and 12.00 hours (within ± 45 minutes) hours after the dosing, before the check-out and at the time of each ambulatory sample collection in each study period.

The subjects' well-being (assessed by verbal questionnaire to gather information about AEs) will be asked at the time of the medical examination, during the vital signs recording and at the time of each ambulatory sample collection in each study period; this will be registered in the respective source document.

Seven (7) to 9 days after the collection of 72-h blood sample in second period or after the withdrawal, a telephone call will be made to each subject by the personnel designated by the PI to monitor any serious adverse event, specifically, subjects will be questioned about any symptoms related to COVID-19.

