	
Nevertheless, it may also be performed at any time during the study conduction if judged necessary by the physician.
 
Physical examination will be performed before check-in of each study period and may also be performed at any time during the study conduction if judged necessary by the physician.
 
Vital signs (sitting blood pressure, pulse rate, respiratory rate and axillary-body temperature) will be measured and registered at the time of check-in, prior to dosing, at 03.00, 05.00 and 12.00 hours (within ± 45 minutes) after the dosing, before the check-out and at the time of each ambulatory sample collection in each study period.
 
The subjects' well-being will be asked at the time of the medical examination, during the vital signs recording and at the time of each ambulatory sample collection in each study period; this will be registered in the respective source document.
 
Seven (7) to 9 days after the collection of 72-h blood sample in second period or after the withdrawal, a telephone call will be made to each subject by the personnel designated by the PI to monitor any serious adverse event, specifically, subjects will be questioned about any symptoms related to COVID-19.

Bioanalysis	
The concentration of Paroxetine in plasma samples collected during the study will be quantified using a validated bioanalytical UPLC/MS-MS method (LOQ - 0.106 ng/mL) according to COFEPRIS guidelines, GLP and in-house SOPs.
 
Method validation and subject sample analysis will be performed using same anticoagulant (K₂-EDTA) that will be used for blood sample collection in clinical phase.

Bioequivalence Pivotal Study Protocol of Paroxetine tablets 20 mg under fasting conditions.

Pharmacokinetic Parameters	
Employing the observed concentration vs. time profiles of Paroxetine and using WinNonlin® software (version 6.4 or higher), the following pharmacokinetic parameters will be calculated:
 
 • Primary Variables: C_{max} and $AUC_{0-t.}$, • Secondary Variables: AUC_{0-inf}, $AUC_{\%}$ Extrapol, T_{max}, K_{el}, $t_{1/2}$.
Statistical Analysis	
Descriptive statistics will be calculated. Statistical analysis will be performed by using ANOVA on ln-transformed pharmacokinetic parameters C_{max} and $AUC_{0-t.}$. The statistical model used in this research is a general linear model and the same is covered in protocol section 14.3

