- Put patient's life in risk or results in death.

Bioequivalence Pivotal Study Protocol of Paroxetine tablets 20 mg under fasting conditions.

- Requires in-patient hospitalization or prolongation of existing hospitalization.
- Results in persistent or significant disability/incapacity.
- Is a congenital anomaly/birth defect.
- Other important medical events: events that may not be immediately life-threatening or result in death or hospitalization, but may jeopardize the patient or may require intervention to prevent one of the other outcomes listed in the definition.

• Identification of Adverse Events

The subjects will be monitored throughout the study for any adverse event manifestation. They will be encouraged to report any sign, symptom, and any health change to the clinical staff. The severity of each AE and its relationship to the study treatments will be determined by the PI based on observation and questioning of the subjects and in accordance to the following classification: non-assessable or unclassifiable, conditional or unclassifiable, unlikely, possible, probable or certain.

The following measures will be employed to ensure that the adverse event is detected at the earliest:

- The physical examination and vital signs recording will be performed at regular intervals after the study drug administration.
- The subjects' well-being will be enquired at regular intervals (see section 11.1).
- All subjects who have received at least a single dose of the study drug will undergo a complete medical evaluation after the completion of the last sample collection for safety reasons.

Bioequivalence Pivotal Study Protocol of Paroxetine tablets 20 mg under fasting conditions.**• Management of Adverse Events**

A medically qualified designee will be available round-the-clock during the period of housing at the clinical facility. If any subject develops an AE the following measures will be adopted:

- Subject will be evaluated by the physician or designated personnel, treated and/or followed-up until the symptoms disappear or laboratory values return to normal levels, as judged by the PI.
- In case of a SAE, subject will be treated by a physician in the ICU, fully equipped with all the emergency handling material like defibrillator, ventilation mask, ECG machine, suction apparatus, etc., or may be referred to the contract hospital.

• Recording of Adverse Events

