Any symptom, sign or significant abnormal laboratory finding (after repeat test confirms the abnormality) whether observed or reported during the course of the study (i.e., within 7 to 9 days after the last sample collection or after the withdrawal) will be recorded as an adverse event whether it has a causal relationship with the drug or not.

The following information has to be individually recorded for each AE in an Adverse Event reporting form:

- Description of the AE.
- Subject number, period, date and time of last dosing.
- Type of adverse event.
- Seriousness of adverse event.
- Date and time of onset/reporting.
- Date and time of resolution.
- Intensity (mild, moderate or severe).

Bioequivalence Pivotal Study Protocol of Paroxetine tablets 20 mg under fasting conditions.

- Relatedness to the study medication (non-assessable or unclassifiable, conditional or unclassifiable, unlikely, possible, probable or certain).
- Action taken or treatment given.
- Outcome of adverse event (resolved or unresolved).
- Follow-up.
- Further details of the AE (if any).

Severity (Intensity) of the adverse event, adverse reaction suspicion and adverse reactions, will be classified according to the clinical manifestation as:

Mild: Signs and symptoms easily tolerable, which do not need treatment, do not prolong hospitalization and do not require medicine product suspension.

Moderate: Interferes with usual activities (may cause work or school casualties), without directly threatening the patient's life. It requires pharmacological treatment and may or may not require the suspension of the causative drug.

Severe: Interferes with usual activities (may cause work or school dropouts). It requires pharmacological treatment and the suspension of the causative drug.

Adverse reactions are classified according to the assessment of causality as (see table 7):

Table 7 Adverse Reaction Classification

Causality Term	Assessment Criteria
Certain	
 • Clinical event, including alterations in laboratory tests, which manifests itself with a plausible temporal sequence in relation to the administration of the drug. • It cannot be explained by the concurrent disease, or by other drugs or substances. • The response to drug suppression (withdrawal) must be clinically plausible.

Bioequivalence Pivotal Study Protocol of Paroxetine tablets 20 mg under fasting conditions.

Causality Term	Assessment Criteria

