	06.50	14:30	14 th blood sample collection
	07.00	15:00	15 th blood sample collection.
	08.00	16:00	16 th blood sample collection, Snacks.
	09.00	17:00	17 th blood sample collection.
	10.00	18:00	18 th blood sample collection.
	12.00	20:00	19 th blood sample collection, Vital signs recording and well-being assessment, Dinner.
2	16.00	00:00	20 th blood sample collection.
	24.00	08:00	21 th blood sample collection. Medical examination with vital signs, well-being assessment and exit from clinics (Check-out).
	36.00	20:00	22 nd blood sample collection, well-being assessment and vital signs recording.
3	48.00	08:00	23 rd blood sample collection, well-being assessment and vital signs recording.
4	72.00	08:00	24 th blood sample collection, well-being assessment and vital signs recording. Final Compensation for subjects (applicable only for period 2).

Seven (7) to 9 days after the collection of 72-h blood sample in second period or after the withdrawal, a telephone call will be made to each subject by the personnel designated by the PI to monitor any serious adverse event, specifically, subjects will be questioned about any symptoms related to COVID-19.

*The schedule of events may change according to the dosing time

Bioequivalence Pivotal Study Protocol of Paroxetine tablets 20 mg under fasting conditions.

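### All adverse events are recorded to 7-9 days after the last sample, but the only contact planned then asks about serious events and COVID-19; the promised final medical evaluation is also unscheduled

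*Protocol*

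**What the plan says.** **Recording window.** Protocol 11.2 (Recording of Adverse Events) treats any symptom, sign or confirmed significant laboratory abnormality as an adverse event, related or not, if it is observed or reported "within 7 to 9 days after the last sample collection or after the withdrawal". There is no restriction to serious events.

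**Planned contact in that window.** There is one telephone call, 7 to 9 days after the period-2 72 h sample or after withdrawal. Protocol 11.1 states its purpose as "to monitor any serious adverse event, specifically, subjects will be questioned about any symptoms related to COVID-19". The synopsis (Safety Assessment) agrees: "a telephone call will be made to each subject by the personnel designated by the PI to monitor any serious adverse event". Attachment II repeats this as its last entry.

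**Spontaneous reporting.** 11.2 (Identification of Adverse Events) says of subjects: "They will be encouraged to report any sign, symptom, and any health change to the clinical staff".

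**Final evaluation.** The same part of 11.2 says that all subjects who received at least one dose "will undergo a complete medical evaluation after the completion of the last sample collection for safety reasons". Protocol 11.1 says that the medical examination "will be performed before check-in, prior to the dosing and before the check-out in each study period". In Attachment II the last one in period 2 is at 24 h: "Medical examination with vital signs, well-being assessment and exit from clinics (Check-out". After the blood sample, the 72 h row has only "well-being assessment and vital signs recording. Final Compensation for subjects".

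**The concern.** There are two separate mismatches.

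1. The recording window covers all adverse events, but the only scheduled question inside its last 7 to 9 days is confined to serious events and COVID-19 symptoms. A caller who follows the protocol need not ask about anything else. Few or no late non-serious events in the report would then partly reflect that nobody asked.

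2. An evaluation promised to every dosed subject has no slot in the schedule. Staff working from Attachment II would not perform it, and staff working from 11.2 would not know when to.

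What is at stake is the secondary objective, safety and tolerability (Protocol 4.2). Non-serious events go to the committees and the sponsor in the final study report, so their completeness matters there. The primary pharmacokinetic comparison does not depend on either point.

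**Working it through.** **Step 1: the plan's own duration.** Protocol 7.6 gives at least 12 days of participation with a 7-day washout. Check-in is day -1 (there is no day 0) and the period-1 dose is on day 1. The period-2 dose is on day 1 + 7 = 8, and the 72 h sample on day 8 + 3 = 11. Day -1 plus days 1 to 11 makes 12 calendar days, so the stated figure reproduces. It stops at the last blood sample and leaves out the follow-up window. Including that window gives 12 + 7 = 19 to 12 + 9 = 21 days, with the call on study day 18 to 20.

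**Step 2: who asks about non-serious events, and when.**

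| Time | Scheduled contact | Scope |
|---|---|---|
| Each period, to 72 h | Medical examinations, vital signs, ambulatory visits | Well-being questionnaire on adverse events (11.1) |
| Between 72 h of period 1 and the period-2 dose | Period-2 check-in | Well-being assessment (Attachment II) |
| After 72 h of period 2 | Telephone call, day 18-20 | Serious events, COVID-19 symptoms |

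Late events after the first dose can be picked up at period-2 check-in. Nothing equivalent follows the second dose. The instruction to return to the facility for any adverse event (11.2, Follow-Up of Adverse Events) is limited to the washout.

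**Step 3: length of the gap, for completers.** Time from first dose to the end of the window is washout + 3 days (72 h) + 7 or 9 days.

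- Washout of 7 days (protocol minimum): 7/(7 + 3 + 7) = 7/17 = 41.2%; 9/(7 + 3 + 9) = 9/19 = 47.4%.
- Washout of 14 days (an assumption, to show sensitivity): 7/24 = 29.2%; 9/26 = 34.6%.

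**Step 4: exposure at the start of the gap.** Protocol 7.2 gives a half-life of about 12 h. At 72 h, 72/12 = 6 half-lives have passed, and 0.5^6 = 1.6% remains under linear kinetics.

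**Step 5: the final evaluation.** Medical examinations scheduled after the last sample: none. The last is at 24 h, which is 72 - 24 = 48 h before it. Taking the last sample to mean the last in-house sample at 24 h does not work: 11.2 starts the 7-9 day window at the last sample, and 11.1 counts the same interval from the 72 h sample.

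**The case against.** **Recording is not soliciting.** The 11.2 window defines what is recorded once observed or reported; it does not promise active questioning. Both texts can be followed as written, so the first point concerns design rather than a strict contradiction. That is fair. But 11.2 also says subjects are monitored for any adverse event throughout the study, which makes the narrower call harder to explain. Spontaneous reporting is passive, and follow-up to resolution helps only with events already known.

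**The evaluation might itself be a contact.** If the 11.2 evaluation took place after the 72 h visit, the call would not be the only one. No such visit is scheduled, so this supports reconciling the text.

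**The evaluation is mandatory anyway.** 11.2 makes it compulsory and nothing in Attachment II cancels it. The 72 h visit includes vital signs and the well-being questionnaire, both of which overlap with a medical examination, and 11.1 allows one at any time if the physician judges it necessary. That narrows the practical gap, but a discretionary examination does not meet a promise made for every dosed subject.

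**Little is likely to be lost.** For completers this stands: exposure is low and the percentage counts days. It does not carry over to withdrawn subjects, whose window runs from withdrawal. Under 8.5, withdrawal may follow vomiting or diarrhoea within 10 h of dosing, which is less than one stated half-life.

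**No bias between products.** With balanced AB and BA sequences, under-counting after period 2 would fall about equally on both. This stands, and it limits the point to completeness.

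**Conclusion.** Both parts hold. After the period-2 72 h visit, no scheduled contact asks about non-serious events other than COVID-19 symptoms, although such events count as recordable for another 7 to 9 days. For completers at the 7-day minimum washout that is 41-47% of the days from first dose, or 29-35% if the washout were 14 days.

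The number of events missed cannot be derived from the documents. Few drug-related ones are expected in completers, assuming the 12 h half-life and linear kinetics. The percentages do not describe withdrawn subjects, who may enter the window sooner after a dose.

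The evaluation promised in 11.2 appears neither among the examination times in 11.1 nor in Attachment II. The Attachment I flowchart was not available in the copy examined, so its absence there is not confirmed.

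The effect is confined to completeness of the secondary safety data. Sample size, error rates and the bioequivalence conclusion do not change. This should be corrected because the remedy is cheap.

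**What to change.** 1. In the synopsis, 11.1 and Attachment II, state that the call asks about any adverse event, serious or non-serious, including COVID-19 symptoms, and align the call script. Narrowing the 11.2 window would also make the texts agree, but at the price of less safety information for a stated objective.

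2. Reconcile 11.2 with 11.1 and Attachment II so that text and schedule agree on whether and when the final evaluation takes place. Which version is intended is for the sponsor and investigator to settle.

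The cost is wording in three places, the call script and one reconciliation. The call is already planned; the only downside of the wider question is a few more minor events to record.
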